4. STATISTICAL METHODOLOGIES

4.1 Sample size:

The sample size for this study is based on the primary efficacy objective and primary biomarker objectives. Based on 150 patients, the maximum half width of the 2-sided 95% CI of the estimated ORR will be within 8%. Additionally, based on 150 patients, there will be at least 80% power to detect a statistical improvement in PFS for bTMB high group vs bTMB low subgroup. The power listed in the table below is based on the following assumptions: the test is 2-sided, significance level is 0.10, both biomarker subgroups have at least 25% of the patients (i.e., 37 or more patients in both groups), median PFS is 4 months for the subgroup with a shorter median PFS, the HR of PFS between the subgroup with a shorter PFS versus the other subgroup is 0.6 or lower, the recruitment duration is one year, the follow-up time from last patient in is 18 months, and the dropout rate is 5%.

n =150	Power		
	Biomarker ≥ 25th percentile vs.< 25th percentile	Biomarker ≥ 50th percentile vs. < 50th percentile	Biomarker ≥ 75th percentile vs. < 75th percentile
0.4	100%	100%	100%
0.5	97%	99%	97%
0.6	83%	92%	84%
0.7	58%	69%	58%

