4.7.1 Primary Biomarker Analyses

K-M curves and a log-rank test will be used to evaluate the differences in PFS between bTMB high versus low groups at 16 and 10 two different cutoff points (i.e. bTMB ≥ 16 vs < 16 , and bTMB ≥ 10 vs < 10). The Gatekeeping testing procedures will be used to test PFS differences at these two primary bTMB cut off points. PFS difference at cutoff point 16 will be tested first. If there is statistical significance in PFS difference bTMB ≥ 16 vs < 16 groups, we will claim statistical significant difference in PFS between bTMB ≥ 16 vs < 16 groups, and we will further test PFS difference at cutoff 10. We can only claim PFS difference between bTMB ≥ 10 vs < 10 groups if both tests for cutoff point 16 and cut off point 10 are statistically significant.

The statistical tests for primary analysis as well as for other analyses comparing efficacy differences between bTMB high group vs low group will be two-sided at a significance level of 0.10. The corresponding bTMB group differences will be estimated and two-sided 90% confidence interval will be provided. All other statistical tests used in the study will be two-sided at level of 0.05. Their corresponding point estimators will be estimated and two-sided 95% confidence interval will be provided.

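### SAP 4.1 gives the power of a single log-rank test; under the gatekeeping in SAP 4.7.1 that figure applies to bTMB ≥16 only, and the 80% floor is not assured for the bTMB ≥10 claim near HR 0.6

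*SAP*

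**What the plan says.** SAP 4.1 opens: "The sample size for this study is based on the primary efficacy objective and primary biomarker objectives". The plural matches SAP 3.2, which lists two primary biomarker comparisons of PFS, at bTMB ≥16 versus <16 and ≥10 versus <10. SAP 4.1 then promises that "there will be at least 80% power to detect a statistical improvement in PFS for bTMB high group vs bTMB low subgroup".

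The conditions attached are:

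- for the test itself, "the test is 2-sided, significance level is 0.10"
- a quarter or more of the sample (37 upwards) on each side of the cut
- a 4-month PFS median in whichever subgroup does worse
- for the effect size, "the HR of PFS between the subgroup with a shorter PFS versus the other subgroup is 0.6 or lower"

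Accrual is one year, follow-up after the last patient in is 18 months, and dropout is 5%. The table covers cuts at the 25th, 50th and 75th percentiles and prints 83%, 92% and 84% at HR 0.6. Section 4.1 mentions neither cutoff 16 nor 10, nor any ordering of tests.

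The ordering is in SAP 4.7.1. Cutoff 16 is tested first, and a difference at 10 may be claimed only "if both tests for cutoff point 16 and cut off point 10 are statistically significant". Protocol 6.1 likewise powers a single comparison.

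**The concern.** A single power statement is offered for two primary comparisons that do not have the same chance of success. The first test in the sequence keeps the full 0.10 level and has the tabulated power for its split. The second must pass its own test and also needs the first to have passed, so its power is the probability that two correlated tests on the same patients both succeed. Section 4.1 does not say that its figures exclude this second condition.

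What is at stake is how a missing ≥10 claim would be read. Someone relying on SAP 4.1 would think the ≥10 objective had at least 80% power, and 92% if 10 fell at the median, whereas part of the chance of failure comes from the gate at 16. In a study meant to judge cutoffs, that difference should be visible in the plan.

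**Working it through.** **Inputs from SAP 4.1.** N=150; two-sided alpha 0.10, so z=1.645; PFS median 4 months in the shorter-PFS group; uniform accrual over 12 months plus 18 months of follow-up; HR 0.6; 5% dropout. The SAP does not say over what period dropout applies, so I show none and 5% per year.

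**Step 1: reproduce the SAP table.** With exponential PFS and hazard λ, follow-up is uniform on 18 to 30 months, so without dropout

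P(event) = 1 − [exp(−18λ) − exp(−30λ)] / (12λ).

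- Low group: λ = ln 2/4 = 0.1733, P = 0.981.
- High group at HR 0.6: λ = 0.1040, P = 0.912.

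With a share p in the high group, events D = 150 × [0.912p + 0.981(1−p)], and

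power = Φ( √(D·p(1−p)) × |ln HR| − 1.645 ).

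For p=0.25: D = 144.6, √(144.6 × 0.1875) × 0.5108 = 2.660, and Φ(1.015) = 84.5%.

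| Cut | High share | SAP, HR 0.6 | No dropout | 5%/year dropout |
|---|---|---|---|---|
| 25th percentile | 75% | 83% | 83.3% | 82.4% |
| 50th percentile | 50% | 92% | 91.9% | 91.3% |
| 75th percentile | 25% | 84% | 84.5% | 83.7% |

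At HR 0.7 the no-dropout formula gives 57.9%, 69.0% and 58.7%, against 58%, 69% and 58% in the SAP. The table is therefore single-test power.

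**Step 2: bounds that need no correlation.** If the two tests have powers a and b, the probability that both succeed lies between a+b−1 and the smaller of a and b. From the SAP's own HR 0.6 figures:

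| Share ≥16 / ≥10 | Lower bound | Upper bound |
|---|---|---|
| 25% / 75% | 0.84+0.83−1 = 67% | 83% |
| 25% / 50% | 0.84+0.92−1 = 76% | 84% |
| 50% / 75% | 0.92+0.83−1 = 75% | 83% |

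**Step 3: joint power.** The groups are nested (everyone at ≥16 is also at ≥10). With shares p16 and p10, the null correlation of the two log-rank statistics is approximately

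ρ = √[ p16(1−p10) / (p10(1−p16)) ].

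Joint power is the bivariate normal probability that both statistics exceed 1.645, using the Step 1 margins with 5%/year dropout. HR is 0.6 at both cutoffs. The shares are my assumptions.

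| Share ≥16 / ≥10 | ρ | Test 16 | Test 10 | Both |
|---|---|---|---|---|
| 25% / 75% | 0.333 | 83.7% | 82.4% | 71.4% |
| 25% / 60% | 0.471 | 83.7% | 90.1% | 78.1% |
| 25% / 50% | 0.577 | 83.7% | 91.3% | 79.6% |
| 50% / 75% | 0.577 | 91.3% | 82.4% | 78.5% |
| 30% / 60% | 0.535 | 87.1% | 90.1% | 81.2% |
| 40% / 60% | 0.667 | 90.5% | 90.1% | 84.8% |

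Ignoring dropout adds about 1 point (72.7% to 85.8% across the same rows).

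**Step 4: cross-check.** Simulating both log-rank tests on the same 150 patients (20,000 trials, 5%/year dropout, hazards set so that the HR is 0.60 at each cutoff) gave joint power of 69.2% (25/75), 76.5% (25/50) and 78.7% (50/75).

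**Step 5: stronger effects.** The Step 3 method at HR 0.55 gives 85% (25/75) to 94% (40/60). At HR 0.5 it gives 94% to 98%.

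**The case against.** **The table is right for what it describes.** It contains no arithmetic error, section 4.1 speaks of one test, and reporting per-test power for a fixed sequence is legitimate. All of this stands. The defect is one of scope: the opening sentence covers both objectives, and nothing restricts the 80% statement to the first test.

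**The floor often holds.** At 30/60 and 40/60 joint power exceeds 80% even at HR 0.6, and at HR 0.55 or lower every pair examined is at about 85% or more. The 71% figure needs both cutoffs to sit at the 25% limit at once. This also stands. But the SAP states its floor for HR 0.6 and for any split down to 25%, so those boundary cases are inside its own conditions.

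**The practical harm is limited.** SAP 4.7.1 provides estimated group differences with 90% intervals, SAP 4.7.2 describes outcomes across many cutoffs, and protocol 6.7.2 calls the study hypothesis-generating. A reader would therefore have an estimate at 10 to look at even if the formal claim were blocked. That reduces the consequence without correcting the power statement.

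**A stronger reading to avoid.** One might infer that if benefit begins at 10 rather than 16, the gate would defeat the ≥10 claim, and count that against SAP 4.1. The documents do not support using it here. In that case the HR at 16 is weaker than 0.6, so the stated power condition is not met for the first test. It would be an argument about testing 16 first, which is a separate design choice.

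**Conclusion.** The point holds, confined to the second primary biomarker objective. The tabulated power applies to the ≥16 test. That the ≥10 claim cannot have more power than either test follows directly from SAP 4.7.1 and needs no assumption. The size of the loss does need assumptions: with HR 0.6 at both cutoffs, N=150 and the shares listed, joint power is about 71% to 85%, so at least 80% is not assured. The pairs 25/50 (79.6%) and 50/75 (78.5%) lie so close to 80% that the handling of dropout matters; 25/75 is clearly below.

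The results do not show that the ≥10 claim always misses 80%: with the same effect at both cutoffs, the floor is met at HR 0.55 or lower for every pair examined. They do not question type I error control, the ORR endpoint or the ≥16 test. The calculation keeps the SAP's N of 150, so it does not depend on how many patients prove biomarker-evaluable.

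**What to change.** In SAP 4.1:

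1. Label the table as the power of a single two-sided 0.10 log-rank test, applying under the gatekeeping to the bTMB ≥16 comparison.
2. Limit the sentence promising at least 80% power to that comparison.
3. Add the joint power for the bTMB ≥10 claim, computed by the sponsor over its own expected shares of patients at ≥16 and ≥10 and its expected hazard ratios at each cutoff, with those inputs stated. The percentages above should not be copied in, because they rest on assumed shares.

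The cost is one short calculation and a few lines of text, and the stated power for the second cutoff may look less favourable. Test order, alpha and sample size do not change.

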4.2 Analysis Populations

Efficacy Analysis Population:

The primary Efficacy analyses will include all patients who receive at least one dose of study drug.

Safety Analysis Population:

The safety analyses will be based on all patients who received any dose of atezolizumab during the study treatment period.

Biomarker Analysis Population:

Biomarker analyses will include all patients who receive at least one dose of study drug and have evaluable baseline biomarker assessment.

4.3 Demographic and Baseline Characteristics

Demographic characteristics, such as age, sex, race/ethnicity, and baseline characteristics, such as weight, BMI, tobacco use history, histology subtype, ECOG performance status, metastatic lung cancer history, prior cancer radiotherapy, and PD-L1 status, will be summarized. Descriptive statistics (mean, median, standard deviation, and range) will be presented for continuous data, and frequencies and percentages will be presented for categorical data.

Demographic and baseline characteristics will be summarized for safety analysis population and possibly additional analysis populations including selected biomarker sub-populations if necessary.

4.4 Analysis of Study Conduct

The number of patients who enroll in, discontinue, or complete the treatment and study will be summarized. Major protocol deviation including enrollment criteria exceptions will be listed and evaluated for their potential effects on the interpretation of study results.

4.5 Efficacy Analyses

The efficacy analysis will be based on Efficacy Analysis Population (see section 4.2)

4.5.1 Primary Efficacy Endpoint

The primary efficacy endpoint of this study is investigator-assessed ORR, defined as the proportion of patients whose confirmed best overall response is either a PR or CR per RECIST v1.1. For this analysis, patients not meeting these criteria, including patients without at least one post-baseline response assessment, will be considered non-responders. An estimate of the ORR from all patients who received study drug and the 95% CI will be calculated by using the Blaker method.

4.5.2 Secondary Efficacy Endpoints

Secondary efficacy endpoints include disease control rate (DCR), duration of response (DOR), and PFS, per RECIST v1.1, and OS. Disease control rate (DCR) is defined as the rate of patients with complete or partial response as best response or stable disease maintained for 24 weeks per RECIST v1.1. DOR will be analyzed for the subset of patients who achieved an objective response. DOR is defined as the time from the initial occurrence of documented CR or PR until documented disease progression as determined by the investigator or death, whichever occurs first. Median and range will be presented for a descriptive summary. Responders with no PD or death, DOR will be censored at last post-baseline tumor assessment. Responders with no post-baseline tumor assessment will be censored at the date of first dose plus 1.

PFS is defined as the time from the first dose of study drug to the time of disease progression or death from any cause during the study, whichever occurs first. Patients who have not experienced disease progression or death at the time of analysis will be censored at the time of the last tumor assessment. Patients with no post-baseline tumor assessment will be censored at the date of first dose plus 1.

OS is defined as the time from the first dose of study drug to the time of death from any cause during the study. Patients who are still alive at the time of analysis will be censored at the date of their last study assessment (for active patients) or at the last date known alive (for patients in follow-up). Patients with no post-baseline assessment will be censored at the date time of first dose plus 1.

PFS and OS of patients in this study will be summarized graphically and with descriptive statistics such as median and landmark PFS by using the Kaplan-Meier (K-M) methodology. The Brookmeyer-Crowley methodology will be used to construct the 95% CI for the median PFS and OS (Brookmeyer and Crowley 1982). K-M methods will also be used to estimate landmark PFS and OS at various time points (i.e., 6, 12, 18, and 24 months), along with the corresponding 95% CI, by using Greenwood's formula.

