4.5.5 Tumor and Response Evaluations

Tumor assessments will be performed at screening and then every 6 weeks (± 7 days) thereafter, regardless of dose delays, for the first 12 months following Cycle 1, Day 1. After 12 months, tumor assessments will be required every 9 weeks (± 7 days) until disease progression or treatment discontinuation. Disease status (complete response [CR], partial response [PR], stable disease, or PD) will be assessed by the investigator with the use of RECIST v1.1 (see [Appendix 4](#)).

The same radiographic procedure used at screening should be used throughout the study (e.g., the same contrast protocol for CT scans). Assessments should be performed by the same evaluator, if possible, to ensure internal consistency across visits. Results must be reviewed by the investigator before dosing at the next cycle. In addition, all radiographic images will be sent to an independent review facility to standardize results and interpretation. Further details on radiographic methods are described in the IRF charter.

Bone scans (Technetium-99m) or sodium fluoride positron emission tomography (NaF-PET) may be performed at screening if clinically indicated. If bone metastases are present at screening and cannot be seen on CT or MRI scans, Technetium-99m or NaF-PET bone scans should be repeated at the discretion of the investigator when complete response is identified in the target disease or when progression in bone is suspected.

Patients who continue treatment beyond radiographic disease progression assessed per RECIST v1.1 should be monitored with a follow-up scan at the next scheduled tumor assessment when the scan frequency is every 6 weeks (± 7 days). If the scan frequency is every 9 weeks, the follow-up scan is recommended at 6 weeks (± 7 days) or earlier if clinically indicated, or per local standard of care.

For patients who discontinue study drug for any reason other than radiographic PD per RECIST v1.1, tumor assessments should continue at the same frequency as would have been followed if the patient had remained on the study drug until radiographic disease progression per RECIST v1.1 (or loss of clinical benefit for patients who continued treatment after disease progression according to RECIST v1.1), withdrawal of consent, death, or study termination by the Sponsor, whichever occurs first.

At the investigator's discretion, tumor assessments may be repeated at any time if PD is suspected.

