4.5.8 On-Study Survival Follow-Up

While in the study, patients will be followed for survival and anti-cancer therapy. Survival follow-up assessments will occur at specified intervals until study completion or discontinuation. Assessments will include survival status, date of death, cause of death, and any new anti-cancer treatment.

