6.4.2 Secondary Efficacy Endpoints

Secondary efficacy endpoints include OS and investigator (INV)-assessed duration of response (DOR) and PFS per RECIST v1.1.

DOR will be analyzed for the subset of patients who achieved an objective response. DOR is defined as the time from the initial occurrence of documented CR or PR until documented disease progression as determined by the investigator, or death, whichever occurs first. Median and range will be presented for a descriptive summary.

PFS is defined as the time from the first dose of study drug to the time of disease progression or death from any cause during the study, whichever occurs first. Patients who have not experienced disease progression or death at the time of analysis will be censored at the time of the last tumor assessment. Patients with no post-baseline tumor assessment will be censored at the time of first dose.

OS is defined as the time from the first dose of study drug to the time of death from any cause during the study. Patients who are still alive at the time of analysis will be censored at the time of their last study assessment (for active patients) or at the last date known alive (for patients in follow-up).

PFS and OS of patients in this study will be summarized graphically and with descriptive statistics such as median and landmark PFS by using the Kaplan-Meier (K-M) methodology. The Brookmeyer-Crowley methodology will be used to construct the 95% CI for the median PFS and OS (Brookmeyer and Crowley 1982). K-M methods will also be used to estimate landmark PFS, along with the corresponding 95% CI, by using Greenwood's formula.

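### The PFS rules conflict for a patient who dies before any post-baseline scan: the definition counts the death as an event, but the no-scan sentence, taken literally, censors the patient at day 1.

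*SAP*

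**What the plan says.** SAP 4.5.2 deals with PFS in three consecutive sentences.

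1. Definition: PFS runs from first dose to "the time of disease progression or death from any cause during the study, whichever occurs first". A death needs no scan to count.
2. General censoring: "Patients who have not experienced disease progression or death at the time of analysis will be censored at the time of the last tumor assessment". This is expressly limited to event-free patients.
3. No-scan censoring: "Patients with no post-baseline tumor assessment will be censored at the date of first dose plus 1". This carries no such limit.

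Protocol 6.4.2 has the same three steps; its third reads "Patients with no post-baseline tumor assessment will be censored at the time of first dose".

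The OS paragraph of SAP 4.5.2 ends with a sentence of the same unqualified form: "Patients with no post-baseline assessment will be censored at the date time of first dose plus 1".

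Two other places bear on the point. Protocol 4.5.5 sets the scan schedule ("Tumor assessments will be performed at screening and then every 6 weeks", with a 7-day window), so the first post-baseline scan falls at about week 6. Protocol 4.5.8 shows that the information needed to count these deaths is collected: "Assessments will include survival status, date of death, cause of death, and any new anti-cancer treatment".

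**The concern.** A patient who dies at, say, week 4 with no scan since baseline is an event at week 4 under sentence 1 and is censored at day 1 under sentence 3. The documents do not rank the two sentences, and no sensitivity analysis covers the case. Two programmers could follow the text and produce different PFS data sets.

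The variable matters beyond the secondary endpoint list. SAP 4.7.1 bases the primary biomarker analysis on log-rank tests of PFS at bTMB cutoffs 16 and 10, and the power table in SAP 4.1 is a PFS table. Median and 6-, 9- and 12-month PFS are also reported by bTMB group (SAP 4.7.2). Under the literal reading, the patients who fare worst would leave the risk set on day 1 as if nothing were known about them.

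**Working it through.** **1. The plan's own power figure.** Inputs from SAP 4.1: n = 150, two-sided level 0.10, median 4 months in the shorter-PFS group, hazard ratio 0.6, 12 months of accrual, 18 months of follow-up after the last patient. Power = Φ(√(d·p(1−p))·|ln HR| − 1.645), where d is the expected number of events and p the share in one group. Without dropout:

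| Cut | d | √(d·p(1−p)) | × 0.511 − 1.645 | Power | SAP |
|---|---|---|---|---|---|
| 25th percentile | 139.4 | 5.11 | 0.97 | 83% | 83% |
| 50th | 142.0 | 5.96 | 1.40 | 92% | 92% |
| 75th | 144.6 | 5.21 | 1.01 | 84% | 84% |

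With 5% dropout, taken either as a yearly hazard or as a 5% cut in n, results stay within 2 points of the SAP. The table is sound, so its assumptions can be used below.

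**2. Effect on the PFS level.** Let q be the share of patients who die before the first scan with no scan done. The documents do not give q; 2% to 10% is an assumption (3 to 15 of 150 patients). Put the first scan at w = 42/30.4375 = 1.38 months. Let the other patients have constant hazard h after w, chosen so that the true median is 4 months:

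- (1−q)·exp(−h(4−w)) = 0.5, so h = ln((1−q)/0.5)/2.62.
- Counting deaths as events: S(t) = (1−q)·exp(−h(t−w)) for t > w.
- Literal reading: the early deaths leave the risk set on day 1, so S(t) = exp(−h(t−w)). The curve is multiplied by 1/(1−q), and the median becomes w + ln 2/h.

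| q | h | Median, event | Median, literal | 6-month PFS, event | 6-month PFS, literal |
|---|---|---|---|---|---|
| 2% | 0.257 | 4.0 | 1.38 + 2.70 = 4.1 | 29.9% | 30.5% |
| 5% | 0.245 | 4.0 | 1.38 + 2.83 = 4.2 | 30.6% | 32.2% |
| 10% | 0.224 | 4.0 | 1.38 + 3.09 = 4.5 | 31.9% | 35.5% |

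Simulated Kaplan-Meier curves agree to within 0.1 point. Because 1/(1−q) exceeds 1, the shift is upward for any q above zero.

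**3. Effect on the hazard ratio.** Take exponential PFS with median 4 months in the bTMB-low group and hazard ratio 0.6. The cumulative hazard to week 6 is 0.1733 × 1.38 = 0.239 (low) and 0.6 × 0.239 = 0.143 (high). Let the early deaths be part of these events. The literal reading changes each figure to itself plus ln(1−q). After week 6 the ratio stays 0.6.

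| Early deaths, low / high | Low | High | Ratio before week 6 | Direction |
|---|---|---|---|---|
| 10% / 10% | 0.239 − 0.105 = 0.134 | 0.143 − 0.105 = 0.038 | 0.28 | away from 1 |
| 10% / 6% | 0.134 | 0.143 − 0.062 = 0.082 | 0.61 | almost unchanged |
| 10% / 3% | 0.134 | 0.143 − 0.030 = 0.113 | 0.84 | toward 1 |

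**4. Effect on power.** Log-rank simulation: 4,000 trials per scenario, n = 150, hazard ratio 0.6, SAP accrual and follow-up, 5% yearly dropout. Both readings were applied to the same simulated trials.

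| Early deaths, low / high | 25% bTMB-high: event → literal | 50% bTMB-high: event → literal |
|---|---|---|
| 2% / 2% | 82.0% → 82.2% | 91.9% → 92.2% |
| 5% / 5% | 81.1% → 83.0% | 90.9% → 92.1% |
| 10% / 10% | 82.3% → 85.5% | 91.9% → 94.1% |
| 10% / 6% | 81.8% → 78.1% | 91.3% → 88.2% |

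With 25% bTMB-high, the literal reading removes about 3, 7.5 and 15 of about 141 events in the first three rows and 13.5 in the last. Power rises slightly when early deaths are equally common in both groups. It falls by 3 to 4 points when they follow roughly the 0.6 hazard ratio.

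**The case against.** The strongest reply is that the three sentences form a sequence. Sentence 2 needs the date of a last tumor assessment, and sentence 3 supplies a date when none exists, so sentence 3 is a sub-case of the event-free patients in sentence 2. A patient who died already has an event under sentence 1. The OS paragraph supports this: its closing sentence has the same unqualified form and, read literally, could censor deaths in an overall survival analysis, which nobody can have intended. The duration-of-response paragraph follows the same pattern after an explicit event-free condition.

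This stands as an account of the probable intent. A reader might infer from the no-scan sentence that the plan discards early deaths; the documents do not support that. They do not exclude it either, and the authors wrote the event-free condition into the general PFS rule and the duration-of-response rule but left it out here.

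A reader might also infer that the bTMB hazard ratio is pulled toward 1 and that power drops materially. That does not follow. Laying early deaths of 10% and 3% on top of a hazard ratio of 0.6 in 120 patients can show power falling from 81% to 73%. But the starting hazard ratio there is already 0.57, so part of the loss is the removal of an effect that was added, and no document gives those shares. With equal shares, power rises.

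The scope is also narrow. Only deaths with no post-baseline scan at all are affected, and eligibility is limited to ECOG 0 or 1 with adequate organ function. ORR, the primary efficacy endpoint, already counts patients without a post-baseline assessment as non-responders.

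**Conclusion.** The PFS text in both documents contradicts itself for a patient who dies without a post-baseline scan, and the ambiguity reaches the primary biomarker test. The intended meaning is probably that such a death is an event. The fault is that the text leaves this to be guessed and can be programmed the other way.

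The one consistent consequence of the literal reading is an upward bias in the PFS curve. With a true median of 4.0 months, the median becomes about 4.1, 4.2 or 4.5 months at early-death shares of 2%, 5% or 10%. These shares are assumptions, and the figures also assume a constant hazard after week 6. The direction of the effect on the hazard ratio and power depends on the split of early deaths between bTMB groups, so no fixed loss can be claimed. The correction should be made before PFS is programmed.

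**What to change.** In SAP 4.5.2 and Protocol 6.4.2, replace the no-scan sentence for PFS with wording such as: *A patient who has not died and has no post-baseline tumor assessment is censored at first dose plus 1 day. A death without a post-baseline assessment is a PFS event on the date of death.*

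Use the same censoring date in both documents; the present one-day difference (first dose against first dose plus 1) is immaterial but should not remain. Add the same restriction to patients who have not died to the closing OS sentence in SAP 4.5.2.

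The cost is about one sentence per document plus a clause for OS. No new data, visits or analyses are needed, since death dates are already collected, and the change agrees with the PFS definition already in the plan.

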6. STATISTICAL CONSIDERATIONS AND ANALYSIS PLAN

There will be approximately 150 patients enrolled in the study. Safety analyses will include all patients who receive at least one dose of study drug. Biomarker analyses will include all patients who received at least one dose of study drug and have baseline biomarker assessment. The primary efficacy analysis measured by ORR and the primary biomarker analysis will be performed after all patients complete 6 months of follow-up (i.e., 6 months after the final patient has been enrolled). The final analysis will be performed at the end of the study, 18 months after all patients have been enrolled. *The overall survival analysis will be updated once the long-term follow-up data is available, and will be summarized in a separate report. Safety reporting for patients who remain on study drug will also be included.*

In addition, OS data collected through the external death registry data after study completion during the optional long-term follow-up will be updated periodically (e.g., every 1–2 years) based on data availability.

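### The SAP's day-1 censoring rule for OS carries no condition on being alive, so read literally it censors a recorded early death

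*SAP*

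**What the plan says.** SAP 4.5.2 puts no visit condition on the OS event: "OS is defined as the time from the first dose of study drug to the time of death from any cause during the study". Patients still alive are censored at their last study assessment if active, "or at the last date known alive (for patients in follow-up"). A further sentence follows: "Patients with no post-baseline assessment will be censored at the date time of first dose plus 1". It is not limited to living patients or to patients without later contact, and no order of precedence is given. By contrast, the sentence just before it is limited to patients still alive. The first DOR censoring sentence in the same section is limited to responders without progression or death. The PFS counterpart names the kind of assessment, "Patients with no post-baseline tumor assessment will be censored at the date of first dose plus 1", whereas the OS sentence does not.

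Protocol 6.4.2 has only the rule for living patients: "Patients who are still alive at the time of analysis will be censored at the time of their last study assessment (for active patients"), with the last date known alive for those in follow-up. Its default of censoring at first dose is given for PFS and not for OS.

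On data collection, Protocol 4.5.8 says "Survival follow-up assessments will occur at specified intervals until study completion or discontinuation" and "Assessments will include survival status, date of death, cause of death, and any new anti-cancer treatment".

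**The concern.** OS needs a date of death or a date last known alive. It does not need a visit or a scan. A program that follows the SAP sentence as written would test for a post-baseline assessment, find none, and assign one day of censored follow-up, whatever date of death is on file. Kaplan-Meier then treats that patient as if survival would have matched everyone else's.

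This would affect the secondary OS summaries: the median, the landmark estimates at 6, 12, 18 and 24 months, and OS by bTMB cutoff under SAP 4.7.2, where groups are smaller and each lost death weighs more.

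**Working it through.** **Can such a patient arise?** Take a patient who receives Cycle 1 and dies before Cycle 2.

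- Protocol Appendix 1a puts the next dosing visit at 21 (±3) days, the first scan at 6 weeks (±7 days), and on-study follow-up at 3-month intervals.
- Under Protocol 5.3.5.8, a death attributed solely to NSCLC goes on the Study Completion/Study Discontinuation eCRF; other on-study deaths go on the Adverse Event eCRF.

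The date of death can therefore be in the database with no scheduled visit after Cycle 1 Day 1. The event definition makes this patient an event. The last OS sentence, taken literally, makes the same patient a day-1 censoring.

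**How large is the effect?** Neither document gives an OS power, event count or target, so there is no stated figure to reproduce. Inputs:

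- N = 150 (Protocol Section 6: "There will be approximately 150 patients enrolled in the study").
- Median OS in the other patients: 12.5 and 22.6 months (Protocol 3.3.2) and 13.8 months (Protocol 1.2.2.2, atezolizumab arm of the Phase III comparison with docetaxel). These are illustrations, not predictions.
- Exponential survival: assumed.
- m, the number with no post-baseline assessment: not in the documents; assumed 1, 3 or 8.

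Let S0(t) = exp(−ln 2 × t / median). At 12 months this is 51.4%, 54.7% and 69.2% for medians of 12.5, 13.8 and 22.6 months. Under the literal rule the m patients leave the risk set at day 1, so the expected estimate is S0(t).

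- Case A, all m died early and are counted: (1 − m/N) × S0. The literal rule is too high by (m/N) × S0.
- Case B, all m are known alive past t and are counted: m/N + (1 − m/N) × S0. The literal rule is too low by (m/N) × (1 − S0).
- In general the error is (m/N) × (S0 − survival of the affected patients).

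Error of the literal rule in 12-month OS, in percentage points, across the three medians:

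| m of 150 | Case A (all died early) | Case B (all known alive) |
|---|---|---|
| 1 | +0.3 to +0.5 | −0.2 to −0.3 |
| 3 | +1.0 to +1.4 | −0.6 to −1.0 |
| 8 | +2.7 to +3.7 | −1.6 to −2.6 |

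Worked line for m = 8 and median 13.8 months:

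- Case A: 8/150 × 54.7% = 2.9 points. The literal rule gives 54.7% against 51.8%, and a median of 13.8 against 12.7 months.
- Case B: 8/150 × 45.3% = 2.4 points. The literal rule gives 54.7% against 57.1%, and a median of 13.8 against about 15.0 months.

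A Kaplan-Meier simulation of 2,000 trials at this setting gave 54.9% (literal), 52.0% (deaths counted) and 57.3% (known-alive time counted), in agreement.

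**Smaller bTMB group.** Protocol 6.1 plans for 28 patients in the smaller group; SAP 4.1 assumes at least 37. Applying the 54.7% figure to that group, with assumed counts of early deaths:

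- One censored early death adds 1/28 × 54.7% = 2.0 points, or 1/37 × 54.7% = 1.5 points.
- Three add 3/28 × 54.7% = 5.9 points, or 3/37 × 54.7% = 4.4 points.

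**The case against.** The best defence is that the sentence is only a fallback. The paragraph runs from event, to censoring of the living, to a default, and the PFS paragraph follows the same order. A SAP may add a default that the protocol lacks, so its absence from Protocol 6.4.2 is not in itself a contradiction.

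The wording also helps the sponsor. The OS sentence says assessment, not tumor assessment, and Protocol 4.5.8 treats survival contacts as assessments. A patient with a known-alive date from follow-up then has a post-baseline assessment and falls outside the rule. On the widest reading, even the vital signs that Table 4 of Protocol 4.3.2 requires 30 minutes after the first infusion would count, and the rule would apply to almost nobody.

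Much of this stands. A reader might infer that the SAP tells the analyst to override recorded deaths and known-alive dates. It does not say so, and a fallback for living patients is a plausible intent. A reader might also infer that the sentence overstates OS in general. It does not: only discarded deaths push the estimate up, while discarded known-alive time lowers it or leaves it unchanged. Nor do the documents support any particular share of affected patients or of early deaths among them.

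What the defence does not remove is the gap. The term assessment is undefined here, the condition of being alive is missing where neighbouring sentences have it, and a death before Cycle 2 can be recorded outside survival follow-up.

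**Conclusion.** The point holds as a drafting defect: followed literally, the rule gives a wrong result for an early death recorded without a post-baseline assessment. It should be corrected, but it is not critical. OS is secondary and descriptive. The primary efficacy endpoint (ORR) and the primary biomarker analysis (PFS) do not use this sentence.

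The overall effect is probably small. The Case A column is a worst case, resting on assumed counts, exponential survival and every affected patient dying early. Net overstatement requires that affected patients survive worse than the rest, which is plausible for patients with no post-baseline assessment in advanced NSCLC but is not quantified in the documents. The smaller bTMB group is more sensitive. A distorted comparison between bTMB groups would further require the affected deaths to fall unevenly between them, and no figure is offered for that.

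**What to change.** Replace the last OS censoring sentence in SAP 4.5.2 with: *Any recorded death is an OS event. Patients not known to have died are censored at the last date known alive from any source. First dose plus 1 applies only to patients not known to have died and with no survival information after the first dose.*

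This keeps an explicit default, which simply deleting the sentence would not, and it settles precedence without having to define assessment. The cost is one replaced passage in the SAP and the matching derivation in the analysis program. No new data are needed: deaths and survival status are already collected under Protocol 4.5.8 and 5.3.5.8.
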